15.2 Primary Analysis

The primary efficacy analysis is a comparison of the proportion of subjects in each Arm who have developed PTS, defined as a total score of \geq 5 in the limb ipsilateral to the index DVT on the Villalta PTS Scale (or an ulcer) at the 6-month follow-up visit, or subsequently during the 24 months after randomization. A stratum-adjusted Cochran-Mantel-Haenszel test will be used. All testing will be two-sided, and a p-value of 0.05 or less will be considered statistically significant.

Subjects will also be counted as having PTS if they underwent an unplanned endovascular intervention (PCDT or another intervention) for the treatment of severe symptomatic venous disease in the index leg more than 6 months after randomization and either a) they had a total score of \geq 5 on the Villalta PTS Scale that was performed immediately preceding that intervention, or an ulcer; or b) the Villalta PTS Scale was not performed at that time.

Irrespective of any subsequent post-randomization intervention, all patients will be counted in the treatment arm to which they were originally randomized, per the intention-to-treat principle.

Two data sets will be considered:

15.2.1 Modified Full Analysis Set

The modified full analysis set will consist of all subjects randomized except those who did not have DVT (i.e. violated the inclusion criterion) and those deemed to be not analyzable for that outcome. The Adjudication Committee, without knowledge of treatment allocation, will decide if subjects qualify as valid post-randomization exclusions. For subjects who died, were lost to follow-up, or withdrew consent (i.e. refused to be contacted directly or indirectly) before the 24-

month PTS assessment, (142,143), a number of imputation strategies (Section 15.4.2) will be employed in the sensitivity analysis.

15.2.2 Per-Protocol Set

The per-protocol set includes everyone in the modified full analysis set except for any subjects who meet either of the following criteria: (1) randomized to PCDT but did not have skin puncture for endovascular DVT therapy during the first 7 days post-randomization; or (2) randomized to the Control Arm but had skin puncture for PCDT or endovascular DVT therapy, and/or either systemic or local thrombolytic therapy, during the first 7 days post-randomization.

15.3 Secondary Analyses

Secondary analyses will be performed using both analysis sets. To account for multiple testing, a two-sided p-value of 0.01 or less will be considered statistically significant for all tests (144).

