7.1 Pre-Randomization Anticoagulant Therapy (Subjects in Both Arms)

As current recommendations are to anticoagulate patients with suspected DVT even before diagnostic testing, we expect most enrolled subjects to be anticoagulated before randomization (30). Otherwise-eligible DVT patients who are already anticoagulated are still eligible for the study if their symptom onset was within 14 days. After enrollment, the patient should be anticoagulated with one of the regimens listed in Section 6.1.1. To avoid unnecessary transitions, if the patient was already receiving one of these regimens, the physician is encouraged to simply continue it. In patients receiving UFH, the physician should ensure that dose adjustments are being made per the guidelines in Section 6.1.1.

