7.3.3 Phase 1 - Procedure Initiation

PCDT procedures should be initiated using the following accepted endovascular practices (63):

- 1. The endovascular physician should review the baseline imaging studies, examine the affected lower extremity with ultrasound, and select a primary venous access site.
- 2. An intravenous line should be placed and conscious sedation initiated with continuous monitoring of heart rate, oxygen saturation, blood pressure, and cardiac rhythm.
- 3. Sterile technique must be used during all endovascular procedures.
- 4. Local anesthesia should be injected into the skin over the venous access site(s).
- 5. Catheter access into the deep venous system should then be obtained this must be done using ultrasound-guided puncture (to prevent inadvertent arterial punctures) of the selected lower extremity vein (e.g., the ipsilateral popliteal vein) or the right internal jugular vein. The physician may access additional veins under ultrasound guidance at his/her discretion. The physician is strongly encouraged to choose a venous access strategy that will enable direct treatment of any popliteal and/or below-knee thrombus that is needed to ensure adequate inflow into the proximal veins. The use of the contralateral common femoral vein for access is, however, strongly discouraged. The use of the femoral vein in the mid-thigh is prohibited.
- 6. Real-time fluoroscopic monitoring of catheter/guidewire manipulations should be used.
- 7. A catheter should be advanced into the venous system and a baseline venogram of the proximal veins (popliteal vein through infrarenal IVC) should be obtained with digital imaging and serial hand-injections of 5-10 ml non-ionic iodinated contrast, diluted as needed with normal saline, through the catheter at 10-20 cm intervals. Automated power injection is not permitted. **Note:** As the thrombus extent on the baseline venogram is relevant to the study data analysis, care should be taken to obtain complete imaging of the thrombus extent, even if this requires contrast injections from within non-flowing iliac or femoral venous segments.
- The endovascular physician should examine the venogram. Based upon the presence or absence of good popliteal vein inflow and IVC thrombus, the physician should follow the guidelines provided in Section 6.2.4 to determine which PCDT technique must be used.

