9 SAFETY OUTCOMES

The following safety outcomes will be assessed for each subject over the 24-month period.

- Major bleeding and minor bleeding
- Need for transfusion
- Intracranial bleeding
- Symptomatic pulmonary embolism
- Symptomatic recurrent venous thromboembolism
- Mortality

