15.3.2 Major and Any Bleeding

The proportion of subjects with major bleeding during the 10 days after randomization, and between 11 days and 24 months, will be compared between the two groups using a stratum-adjusted Cochran-Mantel-Haenszel test. A similar comparison will be undertaken for any bleeding (major or minor). The nature of major bleeds (e.g. intracranial, needing surgery or transfusion) will be described. Complications will also be described by outcome according to SIR reporting standards (48,120).

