15.3.3 Deaths

Overall and cause-specific counts of death will be described in the two treatment groups; the overall mortality at 1 month and 24 months will be compared using a stratum-adjusted Cochran-Mantel-Haenszel test. In addition, Kaplan-Meier curves will be estimated for the two treatment arms.

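### The VTE, bleeding and death comparisons leave out randomized subjects later judged not to have had DVT, because Section 15.3 applies to them the two sets that exclude such subjects

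*Protocol*

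**What the plan says.** Protocol Section 15.2 provides for two data sets.

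- **Modified full analysis set (15.2.1).** "The modified full analysis set will consist of all subjects randomized except those who did not have DVT", together with those judged not analyzable for the outcome in question. The Adjudication Committee, unaware of allocation, decides whether each exclusion is valid.
- **Per-protocol set (15.2.2).** "The per-protocol set includes everyone in the modified full analysis set except for any subjects who meet either of the following criteria". The two criteria concern whether endovascular or thrombolytic treatment was received in the first 7 days. This set can only be smaller than the first.

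Section 15.3 then opens: "Secondary analyses will be performed using both analysis sets". The harm comparisons are subsections of 15.3:

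- 15.3.1 compares symptomatic VTE to 24 months.
- 15.3.2 on bleeding: "The proportion of subjects with major bleeding during the 10 days after randomization, and between 11 days and 24 months, will be compared".
- 15.3.3 on death: "the overall mortality at 1 month and 24 months will be compared using a stratum-adjusted" Cochran-Mantel-Haenszel test.

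None of the three names a different population. On data collection, Section 9 says: "The following safety outcomes will be assessed for each subject over the 24-month period".

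**The concern.** If there was no DVT at entry, PTS has little meaning as an outcome, and leaving the subject out of the PTS comparison can be defended. That reasoning does not carry over to harms. A subject randomized on a mistaken diagnosis is still exposed to the assigned strategy. Section 7.1 says of anticoagulation: "we expect most enrolled subjects to be anticoagulated before randomization". A PCDT subject may also have been punctured and given rt-PA before the error is recognized. Treating some patients whose diagnosis later proves wrong is part of what the strategy would do in practice, so a bleed, VTE or death in such a patient belongs in the harm comparison.

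What is at stake is the accuracy of the bleeding, VTE and mortality comparisons between arms. The events are infrequent, so each one carries weight. The direction of the error cannot be predicted. Omitting a subject who had an event lowers that arm's rate, and omitting subjects without events raises it slightly.

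**Working it through.** **1. Does any other section bring these subjects back into the comparisons?**

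| Protocol section | What it governs | Restores them to 15.3.1–15.3.3? |
|---|---|---|
| 9 | Safety outcomes assessed in every subject | No: collection |
| 12.7 | Participation ends only by death or withdrawal | No, but it means their data exist |
| 13.4 | SAEs recorded to 24 months in both arms | No: collection |
| 15.1 | Descriptive rates of major bleeding and PE | No: names no analysis set |
| 15.2 | Intention-to-treat sentence | No: settles the arm a subject counts in, not who is included |
| 15.5 | DSMB review | No: monitoring |

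**2. How many such subjects should there be?** The protocol gives no count, and several safeguards make them rare. DVT must be objectively diagnosed before entry (4.4, 18.5.1). Iliac DVT suspected on ultrasound needs venogram or CT confirmation (Appendix 12). Before PCDT the endovascular physician must "examine the affected lower extremity with ultrasound, and select a primary venous access site" (7.3.3). I therefore assume k = 1 to 5 exclusions in one arm and show the range.

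**3. The protocol's own figures.** 311 evaluable per arm, inflated for 10% loss, gives 311/0.90 = 345.6, so 346 randomized per arm, as stated in 15.1. The stated 95% interval half-width of 2.4 points for a 2% event at 311 per arm is also reproduced approximately: a Wald interval gives 1.96 × √(2 × 0.02 × 0.98/311) = 2.20 points, and a Newcombe interval with 6/311 per arm gives 2.45 points.

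**4. Weight of one event.** Section 15.1 expects 2% in the Control Arm, for major bleeding at 10 days and for symptomatic PE at 3 months.

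- Expected events: 346 × 0.02 = 6.92, about 7. Rate: 7/346 = 2.02%.
- One event: 1/346 = 0.29 points, or 1/7 = 14% of the arm's events.

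**5. Effect of k exclusions in one arm.**

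| k | None had an event: 7/(346 − k) | Change (points) | One had an event: 6/(346 − k) | Change (points) | P(at least one event) = 1 − 0.98^k |
|---|---|---|---|---|---|
| 1 | 2.03% | +0.006 | 1.74% | −0.284 | 2.0% |
| 3 | 2.04% | +0.018 | 1.75% | −0.274 | 5.9% |
| 5 | 2.05% | +0.030 | 1.76% | −0.264 | 9.6% |

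**6. Deaths.** Section 15.1 cites earlier studies with loss to follow-up or death combined of 2.5% and 3.4%. Taking all of that as death gives an upper bound: 346 × 0.025 = 8.65 and 346 × 0.034 = 11.8, or about 9 to 12 deaths per arm. One omitted death would then be at least 1/12 = 8% to 1/9 = 11% of the arm's total.

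**The case against.** The strongest case against runs as follows. A safety or all-randomized set is ordinary SAP content, Section 15.6 promises a SAP, and 15.3 does not say that only these two sets may be used. The exclusion concerns a fact that precedes randomization and is decided without knowledge of allocation, so no bias between arms has been shown. Without an index DVT, a later leg event is not a recurrence, and events long after a refuted diagnosis may say little about either DVT strategy. Harms in these subjects are still recorded, reported and seen by the DSMB. The effect is also tiny: under the assumption above, the chance that no excluded subject had a 2% event is 90% to 98%, and even the unfavorable case moves the rate by about 0.26 to 0.28 points against a half-width of 2.4.

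Much of this stands. Exclusions should be rare, the blinded adjudication is a real protection, the harms are not hidden, and the argument is most compelling for early bleeding.

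Two parts do not stand. First, the protocol is not silent: it names the sets and assigns them to these comparisons. A SAP could add an all-randomized analysis, but nothing in the protocol calls for one or gives it precedence. Second, the recurrence point misses what 15.3.1 counts, which is any symptomatic VTE after randomization, PE included. That is a harm of the assigned strategy whether or not the entry diagnosis was right. Blinded adjudication protects against selective exclusion but does not make the harm count complete.

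**Conclusion.** The concern holds. As written, the VTE, bleeding and death comparisons omit every randomized subject accepted as not having had DVT, and no other section restores them. The expected effect is small and can go either way: 0.01 to 0.03 points upward if no excluded subject had the event, or 0.26 to 0.28 points downward if one did, for an event at 2% and 1 to 5 exclusions in one arm. The number of exclusions is an assumption, and the calculation treats excluded subjects as having the same 2% event rate as the rest. The primary PTS analysis and the sample size are unaffected. The point should be corrected because the events are few and the correction is cheap; it does not threaten the trial's main conclusion.

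**What to change.** Add to Section 15.3:

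> The comparisons in 15.3.1 to 15.3.3 will primarily use all randomized subjects in the arm to which they were randomized, with no exclusion for absent DVT; the modified full and per-protocol sets are supportive for these outcomes.

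Keep the two existing sets for the efficacy outcomes. The cost is one sentence and one extra set of tables from data already being collected. The reported safety figures may shift slightly in either direction.

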1.6.4 Limitations of Early CDT Methods

The above studies support rt-PA's ability to remove acute venous thrombus, resulting in CDT's acceptance as a "salvage" treatment for a small minority of patients with particularly severe DVT manifestations. However, these studies also illustrate why the routine first-line use of CDT in proximal DVT is controversial. In the above studies, monitoring of the prolonged (30-48 hours) infusions needed to achieve clot lysis required intensive care unit (ICU) stays of 1-3 days – the use of these precious hospital resources is a major barrier to routine use of CDT. Also, it has been hypothesized that the prolonged systemic exposure to rt-PA delivered via traditional CDT may have increased the risk of major bleeding (11% in the urokinase registry, 2-5% in studies of low-dose rt-PA), including the rare catastrophic bleeding events (49). Given the absence of a multicenter randomized trial proving that CDT provides a long-term health benefit by preventing PTS, CDT is not recommended for routine treatment of proximal DVT (30). These concerns have prompted the development of methods to minimize systemic exposure to rt-PA during CDT.

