PTS severity on Villalta PTS Scale: A difference as small as 1.25 units can be detected (5-point gradations define severity categories) (98, 111). Ultrasound outcomes: Assuming a 50% risk of deep venous reflux in the Control Arm and 10% inflation for losses due to withdrawal, death, or inadequate exams (rare), 142 subjects will provide 80% power to detect a 50% relative risk reduction for this outcome (alpha = 0.05, two-sided). 128 evaluable subjects will provide 80% power to detect effect sizes of 0.5 for reflux and obstruction on the continuous VSDS scales.

Regarding safety, we will perform a descriptive analysis of the rates of major bleeding and symptomatic PE in the two study Arms. These events are expected to occur infrequently (2% for major bleeding at 10 days and for symptomatic PE at 3 months) in the Control Arm. With 311 evaluable subjects per arm, if 2% of each group experiences an outcome, the 95% confidence interval on the difference of 0% will include an absolute decrease or increase of 2.4%.

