15.3.1 Symptomatic Venous Thromboembolism

The proportion of subjects who develop symptomatic VTE within 24 months post-randomization (subdivided according to whether the event was within the first 10 days, 11 to 30 days, 31 to 90 days, or 91 days to 24 months) will be compared between the two treatment groups using a stratum-adjusted Cochran-Mantel-Haenszel test.

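### The p ≤ 0.01 multiplicity threshold in Protocol 15.3 also covers bleeding, VTE and death, so a moderate bleeding excess could be labelled not significant, and it does not fit the descriptive safety plan in 15.1

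*Protocol*

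**What the plan says.** Section 15.2 sets the level for the primary test: "All testing will be two-sided, and a p-value of 0.05 or less will be considered statistically significant". The opening of section 15.3 then sets a stricter level for everything that follows: "To account for multiple testing, a two-sided p-value of 0.01 or less will be considered statistically significant for all tests".

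Three of the subsections that follow are safety comparisons, each using a stratum-adjusted Cochran-Mantel-Haenszel test between arms:

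- 15.3.1: "The proportion of subjects who develop symptomatic VTE within 24 months post-randomization", split into four time windows.
- 15.3.2: "The proportion of subjects with major bleeding during the 10 days after randomization, and between 11 days and 24 months, will be compared", with a similar comparison for any bleeding.
- 15.3.3: "the overall mortality at 1 month and 24 months will be compared".

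Section 9 lists all of these as safety outcomes. None is exempted from the 0.01 rule.

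Section 15.1 describes safety differently: "Regarding safety, we will perform a descriptive analysis of the rates of major bleeding and symptomatic PE in the two study Arms". It expects a 2% Control Arm rate for major bleeding at 10 days and for symptomatic PE at 3 months. It illustrates the precision with 311 evaluable subjects per arm, as a 95% confidence interval reaching 2.4 percentage points either side of zero. That paragraph does not mention death.

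**The concern.** Section 15 gives major bleeding two treatments: a description with precision stated at the 95% level, and a hypothesis test at 0.01. Symptomatic PE is in the same position, because it enters 15.3.1 as part of VTE. The two can disagree about one result: the 95% interval for the difference can exclude zero while the test is called not significant.

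The direction of the error also matters. A multiplicity penalty guards against false positive claims. Applied to a harm, it makes a missed excess more likely, and bleeding is the main known harm of this intervention. Section 1.6.4 cites major bleeding rates of "11% in the urokinase registry, 2-5% in studies of low-dose rt-PA". Section 1.6.7 frames the trial's question as whether PCDT prevents PTS with acceptable safety. A bleeding excess reported as not significant would weigh on that judgement.

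**Working it through.** **Inputs from the protocol.** Control Arm rate 2% (15.1); 346 randomized and 311 evaluable per arm (15.1); two-sided 0.05 for the primary test (15.2); two-sided 0.01 for secondary tests (15.3).

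**Assumption.** The protocol states no major bleeding rate for the PCDT arm, so a range of 3% to 10% is used. The low-dose rt-PA range in 1.6.4 ends at 5%, and the urokinase registry figure there is 11%.

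**Step 1: reproduce the plan's own figure.** 2% of 311 is about 6 events per arm, p = 6/311 = 0.0193. The Wilson 95% limits are 0.0089 and 0.0414. The Newcombe half-width for a difference of zero is √[(u − p)² + (p − l)²] = √(0.0222² + 0.0104²) = 0.0245, or 2.45 points. The stated 2.4 reproduces. (The Wald half-width is 1.96 × √(2 × 0.02 × 0.98/311) = 2.20 points.)

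**Step 2: power to declare a bleeding excess.** For each pair of true rates, all pairs of binomial counts are enumerated, and the probability of every pair whose unstratified Pearson chi-square is significant is summed. The statistic is z = (p₁ − p₀)/√[2·p̄(1 − p̄)/n], compared with 1.960 (level 0.05) or 2.576 (level 0.01).

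| True PCDT rate (assumed) vs 2% | 346 per arm, 0.05 | 346 per arm, 0.01 | 311 per arm, 0.05 | 311 per arm, 0.01 |
|---|---|---|---|---|
| 3% | 13% | 3% | 13% | 3% |
| 4% | 34% | 14% | 31% | 11% |
| 5% | 59% | 33% | 54% | 28% |
| 6% | 79% | 55% | 74% | 49% |
| 7% | 91% | 75% | 88% | 69% |
| 8% | 97% | 88% | 95% | 84% |
| 10% | 99.7% | 98% | 99% | 97% |

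At 346 per arm the loss is 26 points at 5% (59 − 33), 24 points at 6% (79 − 55) and 9 points at 8% (97 − 88).

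**Step 3: observed results that fall in the gap.** The interval is Wald: d ± 1.96 × √[p₀(1 − p₀)/n + p₁(1 − p₁)/n].

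| Control | PCDT | Chi-square p | 95% CI for the difference (points) | Label at 0.01 |
|---|---|---|---|---|
| 6/311 (1.9%) | 15/311 (4.8%) | 0.046 | 0.1 to 5.7 | not significant |
| 6/311 (1.9%) | 18/311 (5.8%) | 0.0125 | 0.8 to 6.9 | not significant |
| 6/311 (1.9%) | 19/311 (6.1%) | 0.008 | 1.1 to 7.2 | significant |
| 7/346 (2.0%) | 20/346 (5.8%) | 0.0107 | 0.9 to 6.6 | not significant |

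With 311 per arm and 6 control events, 15 to 18 PCDT events have a 95% interval that excludes zero but miss the 0.01 threshold. From 19 events the result is significant on either rule.

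All of these p-values ignore the stratification of the planned test, so the exact cut-points may move slightly.

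**The case against.** The case against has several parts.

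- **No split between benefit and harm.** A reader might infer that efficacy is judged at 0.05 and harm at 0.01, so that the plan favours PCDT. The text does not support this. Only the single primary test is at 0.05. Quality of life, PTS severity, the composite and acute symptoms are all at 0.01 too. The rule is two-sided, so it equally restrains a claim of less VTE or fewer deaths with PCDT. This part stands.
- **Large excesses are still found.** A reader might infer that any real bleeding excess would be declared not significant. It would not: at a true 8%, power at 0.01 is 88% with 346 per arm. The gap concerns moderate excesses, and the PCDT rates are assumptions. This also stands.
- **The conflict with 15.1 is limited.** Section 15.1 names major bleeding and symptomatic PE, not death, and it gives the 95% interval as a statement of precision, not as a required reporting format. This stands, although death remains under the 0.01 rule through 15.3.3.
- **The threshold does not decide safety during the trial.** Under 15.5 the DSMB acts on an overall assessment of risk and benefit, with no p-value threshold, and can ask for unblinding at any stage. Counts and rates would stay visible in any report. This limits the consequence to final labelling and conclusions.
- **Adjusting safety tests is a judgement.** The safety comparisons are numerous, over several windows and both analysis sets, and testing all of them at 0.05 has a cost in false signals. This is fair, and is the price of the fix. It does not explain why 15.1 and 15.3 differ, or why a rule against false positives should extend to the main expected harm. Low event counts also limit detection: at a true 5%, power is only 59% even at 0.05. The stricter level takes it down to 33%.

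**Conclusion.** The point holds in a limited form. As worded, the 0.01 rule covers the VTE, bleeding and mortality comparisons. For major bleeding and symptomatic PE it does not fit the descriptive approach of 15.1. Its effect on harms is to raise the chance that a moderate excess is labelled not significant, even when the 95% interval excludes zero.

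The size rests on the protocol's 2% control rate, on assumed PCDT rates, and on an unstratified chi-square test. On that basis about a quarter of the chance of declaring an excess is lost, in absolute terms, at true rates of 5% to 6%, and much less at 8% and above. The documents do not show a plan that sets a lower bar for benefit than for harm among secondary outcomes, or one that would hide a large excess. The consequence lies in how final results are labelled and interpreted. The change is worth making because it is cheap.

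**What to change.** State in 15.3 that the 0.01 threshold applies to secondary efficacy outcomes only. Have the bleeding, PE/VTE and death comparisons reported as between-arm differences with 95% confidence intervals and p-values not adjusted for multiplicity. Align 15.1 and 15.3 so that major bleeding and symptomatic PE have one stated approach, and say in 15.1 that death follows it as well.

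This takes a sentence or two and changes nothing in sample size, data collection or conduct. The downside is a somewhat higher chance of a false safety signal, given the number of safety comparisons. Reporting intervals alongside the p-values helps readers to weigh this.
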